The secondary outcome measure is patient-reported outcome (PRO) assessed with reliable and validated rating-scales (0-100 points); EuroQol (EQ-5D-5L), the Achilles Tendon total Rupture Score (ATRS), foot and ankle outcome score (FAOS), and Olerud-Molander Ankle Score (OMAS) at 6 and 12 months. Data of both groups (IPC vs. no IPC) will be presented by mean, median, standard deviation, and range. EQ-5D-5L is a validated, generic health-related quality of life measure consisting of five items each with a five-level answer possibility. Each combination of answers is converted into a health index score¹⁷. The EQ5D-index is measured on an interval scale and, thus, analyzed with parametrical statistics. ATRS (ordinal scale) is a validated ATR PRO measure¹⁸, while OMAS (ordinal scale) and FAOS (ratio scale) are validated for ankle fractures¹⁹. Functional evaluation of the ATR-healing will be performed by the validated heel-rise test at one year post-injury^{18 16}. Heel-rise height and work (continuous data) of both groups will be presented²⁰.

Callus production (continuous data) in ATR and ankle fracture (AF) patients will be assessed at six weeks using microdialysis followed by quantification of procollagens, which recently emerged as a method to assess tendon healing^{15 22 23}. For fracture healing quantification of bone formation markers (alkaline phosphatase, osteocalcin, and pro-collagen type I propeptide) will be performed.

VTE-preventive mechanisms will be analyzed at the six week visit by assessments of profibrinolysis and coagulation as well as by blood-flow quantification using ultrasound²⁴. Overall hemostatic potential (OHP), D-dimer, plasminogen activator inhibitor-1 (PAI-1), endogen trombin potential, trombin antitrombin complex, plasmin antiplasmin complex, tissue plasminogen activator/PAI complex will be assessed at Karolinska Institutet, Coag. Unit, Ass. Prof. [name]. Peak femoral blood velocity will be calculated using custom ultrasound software and compared with baseline values, while microcirculation and tissue oxygenation will be assessed by near-infrared spectroscopy (INVOS®)^{25 24}. These explanatory continuous data will be compared between the groups.

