Outcome: The primary outcome, VTE at 6 weeks post-immobilization, will best be assessed by screening CDU of DVTs. CDU is rapidly becoming the investigation of choice to confirm the diagnosis of DVT since it is non invasive. It is acceptable to patients, can easily be repeated several times and uses equipment, which is widely available. Thus consent, accrual and adherence in a trial are likely to be more easily achieved than with alternatives.

The primary outcome will be validated by the explanatory outcome of VTE-prevention, assessed by quantification of blood flow, profibrinolysis and coagulation factors from blood serum taken by a study nurse at the 6 weeks visit.

A long-term effect of IPC on VTE and healing will be confirmed by the secondary patient-reported outcome measures (PROM). We have data suggesting that an asymptomatic DVT affects PROM at 1 year¹⁶. The PROM will be assessed by the patient filling in the validated questionnaires (EQ-5D-5L, ATRS, FAOS, OMAS) at the 1 year visit at the physiotherapist, who will also perform the functional evaluations, i.e. heel-rise tests. If any patient will miss the 1 year visit, the questionnaires will be sent home to the patient.

An IPC effect on tissue healing will be corroborated by assessment of callus production. Callus production in ATR and AF patients is assessed at 6 weeks by microdialysis followed by quantification of procollagens¹⁵.

To further control that the outcome measures are registered correctly, independent data monitoring and help with data management will be performed by eg. Karolinska Trial Alliance (KTA). Major outcome events (including serious adverse events believed to be due to treatment) will be supplied. All data will be reported using an online system registration at Karolinska Institutet called RedCap, which is a validated patient reporting tool used at over 300 universities.

Trial Organization: The Steering Committee will consist of [name] (PI), [name] (VTE expert), [name] (VTE expert), [name] (Radiologist, compression Doppler ultrasound), [name] (Statistician), [name] (coordinating study nurse), [name] (bone healing), [name] (expert on patient-reported outcome), and [name] (Patient representative).

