The mean inclusion per hospital is (one)-two AF each week and one ATR every second week, which totals at least a mean of 75 patients/hospital/year⁹. With 1,5 patients included per week per each hospital (20 hospitals registered), we will finish inclusion within one year.

For the secondary patient-reported outcomes, the trial has more than 95% power (alpha 0.05) to identify a clinically relevant difference, which at one year is 10 points difference on the rating scales (0-100)²⁰. For the explanatory VTE-preventive mechanisms (blood serum test) and collagen production (microdialysis) earlier studies demonstrate that a sample size of 100 gives 90% power to detect significant differences between groups, which will save expenses.

Treatment compliance of the patients, which was 91% in our earlier study, will be registered both by the IPC-device and by the patient. Patients will daily register the number of hours that IPC was used.

Material: Patient selection – population, sample

Male and female patients aged between 18 and 75 years with an acute injury requiring lower-leg immobilization, i.e. acute unilateral ATR or isolated AF, in a hospital setting will be eligible. The exclusion criteria will be: inability to give informed consent; planned follow-up at another hospital; renal failure; heart failure with pitting oedema; thrombophlebitis; malignancy; peripheral vascular disease; haemophilia/thrombophilia and pregnancy⁹.

The randomising clinician or nurse will screen for eligible patients as soon after their presentation to hospital as possible. To minimize differences between hospitals, patients will be eligible for inclusion if treatment starts within 10 days after the injury. IPC-prophylaxis for

DVT may have greater effect if started early after injury, but these potential differences will also be considered below. The responsible clinician collects the baseline data necessary to complete a randomization form. He/she then will randomize patients via a central, web-based service (RedCap) by giving the baseline data (which are then stored securely) and receives the treatment allocation at the end of the session.

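### Blood serum is the only specimen named for the coagulation and fibrinolysis markers, yet two of the seven cannot be measured in serum and three more would partly reflect clotting in the tube

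*Combined protocol and SAP*

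**What the plan says.** Three parts of the combined protocol and SAP bear on this.

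- **Variables and measures** gives the panel: "Overall hemostatic potential (OHP), D-dimer, plasminogen activator inhibitor-1 (PAI-1), endogen trombin potential, trombin antitrombin complex, plasmin antiplasmin complex", and then "tissue plasminogen activator/PAI complex will be assessed at Karolinska Institutet". That is seven blood markers. The timing is fixed there too: "VTE-preventive mechanisms will be analyzed at the six week visit by assessments of profibrinolysis and coagulation". No specimen is named in that section.
- **Study Design (PICO), Outcome** names the specimen: "profibrinolysis and coagulation factors from blood serum taken by a study nurse at the 6 weeks visit". It also gives the markers a role beyond description: "The primary outcome will be validated by the explanatory outcome of VTE-prevention".
- **Estimated sample size and power** names the specimen a second time, in the sentence that begins "For the explanatory VTE-preventive mechanisms (blood serum test". It sets the sample at 100, said to give 90% power.

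Under **Research question**, one secondary question asks whether compression lowers VTE incidence by raising profibrinolysis. The blood panel is the only planned measurement that addresses it. Plasma, citrate, any other anticoagulant, centrifugation and freezing are not mentioned anywhere.

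**The concern.** Serum is collected by letting the sample clot. Fibrinogen has by then become fibrin, and clotting factors have been consumed. An assay that works by making the sample clot has nothing left to act on, and an assay for a product of clotting picks up what was formed in the tube as well as what circulated in the patient.

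If the stated specimen were collected, part of the panel would give no usable value and part would give values that mix the patient's state with sample handling. A wrong tube cannot be put right after the draw. The loss would fall on the profibrinolysis question and on the blood-marker part of the mechanism evidence that is meant to support the primary result.

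**Working it through.** **Step 1: is any other specimen named?** Setting the three sections side by side:

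| Section | Specimen named for the blood markers |
|---|---|
| Variables and measures | none |
| Study Design (PICO), Outcome | serum |
| Estimated sample size and power | serum |

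The two mentions agree, and nothing elsewhere corrects or qualifies them.

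**Step 2: what can serum yield, marker by marker?** The reasoning uses only what serum is and what each marker measures.

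| Marker | In serum | Reason |
|---|---|---|
| OHP | not obtainable | needs fibrin formation and lysis; fibrinogen is gone |
| Endogenous thrombin potential | not obtainable | needs a clotting system that can still be triggered |
| Thrombin-antithrombin complex | distorted | formed while the sample clots |
| PAI-1 | distorted | released by platelets during clotting |
| tPA/PAI complex | distorted | released PAI-1 binds tPA |
| D-dimer | loss not shown | some effect possible |
| Plasmin-antiplasmin complex | loss not shown | some effect possible |

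Count: 2 + 3 + 2 = 7. Two are unobtainable, three are distorted to an unknown degree, and two are not shown to be lost.

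**Step 3: the plan's own figure.** The 90% power with a sample of 100 cannot be reproduced. No difference, standard deviation, alpha or sidedness is given for any marker, and it is not stated whether 100 is the total or the number per arm. What can be done is to invert the two-means formula, assuming two-sided alpha 0.05 and the plan's 1:1 allocation:

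d = (z for alpha + z for power) × √(2/n per arm) = (1.960 + 1.282) × √(2/n)

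- 100 in total, n = 50 per arm: 3.242 × 0.200 = 0.65 standard deviations.
- 100 per arm: 3.242 × 0.1414 = 0.46 standard deviations.

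The documents give nothing to compare these with, so the figure is neither confirmed nor refuted.

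**Step 4: what added noise would do.** This is an illustration only, since no size for the noise can be taken from the documents. With 50 per arm, power is approximately Φ(d × √(50/2) − 1.960) = Φ(5d − 1.960). If clotting in the tube inflates a marker's standard deviation by a factor k while the true difference is unchanged, d becomes 0.65/k.

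| Assumed k | d | Power |
|---|---|---|
| 1.00 | 0.65 | 0.90 |
| 1.30 | 0.50 | 0.71 |
| 1.625 | 0.40 | 0.52 |

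This applies to the three distorted markers. For the two unobtainable ones there is no comparison to power.

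**The case against.** The strongest reply is that serum is loose wording. The sentence in the outcome part, read literally, also derives blood flow from serum, although flow is measured by ultrasound. The second mention is a label inside a power statement. Neither is a collection instruction, and no specimen in the plan has one. The assays are assigned to a coagulation unit, and the Steering Committee includes VTE experts and a coordinating study nurse. Such a laboratory may well ask for plasma.

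This stands as a plausible account of intent, and it means one cannot say that serum tubes will in fact be drawn. It does not remove the point. Serum is the only specimen stated, it is stated twice, the draw is given to a study nurse, and no laboratory manual is referred to.

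Several stronger readings are tempting, and the documents do not support them:

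- *The profibrinolysis question becomes unanswerable.* D-dimer and plasmin-antiplasmin complex both bear on fibrinolysis and are not shown to be lost. The three distorted markers are degraded, which is not the same as lost.
- *The treatment comparison is biased.* In-tube clotting would occur in both randomized arms, and nothing in the plan suggests that handling differs by arm. The expected effect is reduced sensitivity.
- *All mechanism support for the primary result is lost.* Femoral blood velocity and near-infrared spectroscopy do not depend on the tube.
- *The error would occur at 20 or more hospitals.* The plan limits these tests to a sample of 100 to save cost and does not say which hospitals supply it.
- *One plasma type must be used for all seven assays.* No assay methods are given that would settle this.

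**Conclusion.** The concern holds in a bounded form. The specimen named in the plan is incompatible with two of the seven listed blood markers (OHP and endogenous thrombin potential). It would compromise three more (thrombin-antithrombin complex, PAI-1 and tPA/PAI complex) by an amount that cannot be quantified from the documents, adding noise in both arms. The effect is to weaken the planned evidence on profibrinolysis, which rests on about 100 samples, or about 200 if the stated figure is per arm.

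The ultrasound-based primary endpoint, the blood-flow measures, the microdialysis and patient-reported outcomes, and the 1400-patient sample size are untouched.

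Two assumptions carry the conclusion: that the word serum is used in its ordinary sense, and that sites would follow the text. If plasma was always intended, the correction is one of wording, but it is still needed so that sites and readers of the results know what was measured.

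**What to change.** In the outcome part of the study design section and in the sample size section, replace the reference to serum with anticoagulated (for example citrated) platelet-poor plasma for at least OHP, endogenous thrombin potential, thrombin-antithrombin complex, PAI-1 and tPA/PAI complex. Have the coagulation laboratory confirm the anticoagulant for each of the seven markers, including D-dimer and plasmin-antiplasmin complex. State one rule for centrifugation, freezing and time limits that applies to every site contributing samples. In the outcome sentence, separate blood flow from the blood-sample markers, so that it no longer reads as if flow came from the tube.

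The cost is a short text change, a different tube, and a centrifugation and freezing step at a draw already planned. It adds no visit and leaves the main sample size as it is. If any samples have already been collected, report the specimen actually used. Do not present OHP or endogenous thrombin potential from serum.

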STOP Leg Clots

-

Swedish-international multicenter Trial of Outpatient Prevention of Leg Clots

**Prevention of thromboembolism and failed healing during lower
limb immobilization –
a multicenter study with adjuvant intermittent pneumatic
compression therapy**

Date of document: 200901

Identifiers: NCT03259204 Unique Protocol ID: 2017-00202

STOP Leg Clots -

Swedish-international multicenter Trial of Outpatient Prevention of Leg Clots

Prevention of thromboembolism and failed healing during lower limb immobilization –
a multicenter study with adjuvant intermittent pneumatic compression therapy

Purpose and Aims

Complications related to lower limb immobilization, such as venous thromboembolism (VTE) and delayed healing, after musculoskeletal trauma and reconstructive surgery represent increasing problems. The National Health Service in England has identified prophylaxis of VTE as the number one prioritized intervention^{1 2}.

As a result of trauma and post-operative lower limb immobilization and associated impaired neuro-vascular supply, patients exhibit an increased risk of VTE and hampered healing. Pharmacoprophylaxis for VTE in patients with lower-leg immobilization has, however, demonstrated low or non-effectiveness^{3 4 5}. Thus, there is no consensus for prevention, and a need for novel treatment strategies^{1 2 4}.

Our hypothesis is that leg immobilization calls for promoted blood circulation using adjuvant mechanical compression. This intervention, in the form of intermittent pneumatic compression (IPC) therapy, targets the primary cause of impaired neuro-vascular flow. IPC might reduce the risk of VTE and improve healing by respectively increasing the local supply of anticoagulants and healing mediators.

We aim to demonstrate that adjuvant, outpatient IPC-therapy in lower-leg immobilized patients, compared to treatment-as-usual, reduces VTE-incidence and improves healing. This VTE-preventive intervention can without delay be adapted in daily health care in order to increase patient safety and reduce costs as compared to pharmacological alternatives.

The primary outcome measure is the VTE-incidence at the end of immobilization, i.e. about at six weeks. Secondary outcome measures are patient-reported outcome assessed with validated scores, and effects on healing callus production with microdialysis and levels of profibrinolysis factors.

Survey of the Field

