International guidelines offer opposing recommendations regarding VTE-prevention during leg-immobilization. The American College of Chest Physicians recommends no pharmacologic thromboprophylaxis, low molecular weight heparin (LMWH), due to the increased risk of bleeding in relation to the expected low effect of LMWH⁴. Furthermore, NICE, UK, recommends to consider offering LMHW to leg-immobilized patients after evaluating the risks of VTE and bleeding¹. Thus, today the clinical practice of VTE prevention in leg-immobilization varies considerably^{6 7}, and lacks strong evidence⁵.

The risk of VTE in association with trauma/surgery and leg-immobilization is high, with an estimated deep venous thrombosis (DVT) rate of 25% up to 50% after e.g. Achilles tendon rupture (ATR)^{8 9}. Today it is known that also asymptomatic DVTs often may result in pulmonary embolism¹⁰. Pharmacologic thromboprophylaxis (LMWH) in patients with lower-

leg immobilization has, however, shown to be low- or even non-effective in some studies^{5 7 3 4 11}. The latest meta-analysis of LMWH in leg-immobilized patients show only a moderate prevention on DVT because risk of bias and no preventive effect on pulmonary embolism⁵. Moreover, LMWH exerts adverse effects on the healing process¹² and increases the risk of bleeding complications^{3 4}. Thus, NHS, UK and SBU, Sweden have identified the need to develop safer and more efficient VTE-prophylaxis^{1 2 13}.

Mechanical thromboprophylaxis (IPC) reduces VTE, is a cost-effective intervention in hospitalized patients, and is recommended by guidelines for surgical patients^{1 14}. Whether IPC treatment applied during leg immobilization and performed in an outpatient setting can reduce the incidence of DVT is unknown. Therefore, mechanical thromboprophylaxis is not yet mentioned in guidelines for leg-immobilized patients. Recently, however, we published the first evidence that leg immobilized patients with ATR treated with adjuvant IPC exhibited a DVT-rate of 21% compared to 37% in the controls at 2 weeks. IPC intervention ended at two weeks, and thus at 6 weeks the DVT-rate was 50% in both groups⁹.

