Thus, it remains to show if prolonged adjuvant IPC therapy during the whole 6 weeks immobilization period could reduce the incidence of VTE in leg-immobilized patients, also in patients with fractures. Can the IPC treatment synchronously enhance the healing process so that it will lead to a long-term increased patient-reported outcome? Recent studies suggest that the increased neuro-vascular flow induced by IPC enhances the healing process¹⁵.

Research question

The primary research question is:

- Does addition of IPC to patients with lower limb immobilization in routine care, reduce the incidence of VTE up to the end of immobilization, i.e. 6-8 weeks.

Secondary questions are:

- Can adjuvant IPC during leg immobilization enhance fracture/soft tissue healing and improve patient-reported outcome?
- Does IPC reduce VTE incidence by upregulation of profibrinolysis?

Variables and measures

Primary outcome (binary), VTE, is defined as symptomatic or asymptomatic deep venous thrombosis (DVT) assessed at six weeks of immobilization by screening compression duplex ultrasound (CDU), or symptomatic pulmonary embolism detected by computer tomography. Assessors of CDU will be skilled ultrasonographers, masked to the treatment allocation⁹. The CDU-examination will document absence/presence of thrombus in the calf, popliteal and femoral veins separately, as previously described⁹. All positive examinations and those considered technically difficult will be reviewed by a specially trained vascular physician (blinded to the treatment allocation), who will establish the diagnosis and classify the examination result as absence or presence of thrombus. This will show the incidence of VTE in each group.

We acknowledge that the CDU assessment of DVT will be the dependent measure of outcome since DVT is more common than pulmonary embolism. CDU screening (surrogate outcome), can be justified because of the clinical significance attributed to even asymptomatic DVTs, which today are known to cause a high rate of pulmonary embolism, affect the patient outcome¹⁶ and are treated by most clinicians with anticoagulant therapy¹⁰. To reliably confirm or refute an effect of IPC on survival or clinical pulmonary embolism a

randomized trial would require a sample size of several tens of thousands of patients; this is not currently possible.

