Intervention: There is a need for new VTE prophylactic methods, especially in lower limb immobilized patients. IPC has been demonstrated cost effective both as adjuvant and versus no pharmacoprophylaxis in hospitalized patients by NICE. However, in an outpatient setting there are yet only recent short-term data of the efficacy of IPC. There is a need for data on the efficacy of IPC during long-term leg immobilization to inform guidelines.

The intervention, *addition of IPC to routine care*, will be administered in the emergency department or in the outpatient clinic. Patients will during the six weeks of lower limb immobilization receive bilateral calf IPC (Venaflo Elite, DJO LLC, Vista, CA, USA) applied under an orthosis (Aircast® AirSelect Elite, DJO LLC, Vista, CA, USA). This IPC-system delivers rapid inflation and graduated sequential compression. The IPC device is mobile and should therefore not restrict patient mobilization, but can be taken off if the patient wants to mobilize independently. The patients will be instructed to apply the IPC-therapy continuously, both day and night. Compliance with the treatment will be registered by both the patient and by the device⁹. American College of Chest Physicians recommend that efforts should be made to achieve 18 h of daily compliance with IPC in hospitalized patients¹⁷. However, there are no recommendations for mobile outpatients. Outpatients were in our recent study recommended at least 6h daily therapy, and in this study we will increase the recommendation to 10h/daily. Graduated compression stockings are part of IPC-care and these should be applied and worn under the IPC sleeves on both legs. IPC will be discontinued if the patient declines to continue IPC or had adverse effects of the IPC that warrants removal. At the 2 and 6 weeks visit the orthosis will be removed by a nurse and the patient will be examined by an orthopaedic surgeon (masked to the treatment allocation), who will document compliance and adverse events. At the 6 weeks visit the patient will also be sent for CDU-examination, which will document the main outcome. Patients will during the six weeks leg immobilization be weight-bearing with crutches or non-weight-bearing with crutches according to the preference of the orthopedic surgeon (masked to the treatment allocation). Weight-bearing will be recorded and accounted for in the statistical analysis.

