Comparator: Since there are no documented highly effective therapies for DVT reduction during leg immobilization, and guidelines vary regarding prophylaxis, we chose to use treatment-as-usual as a comparator, regardless of LMHW use or not^{3 4}. Based on our calculations less 10% of the patients will receive LMHW in clinical practice and our power calculations has taken this into account. NICE has stated that LMWH is not a feasible general treatment, especially health economically, during six weeks for all patients with leg immobilization. One review, including 1,490 patients from six randomized trials, showed a small reduction in DVTs using LMHW⁸. However, they concluded that more research is needed to develop more effective and safe thromboprophylactic treatments. Moreover, since a study with LMHW as a comparator would necessitate too many patients - this was not an option. The main research question remains: Is adjuvant IPC more effective than routine care for reducing the incidence of VTE in patients during lower limb immobilization? The usage of no general VTE-prevention in the comparator group is moreover justified since a DVT-screening will be performed on all patients. LMWH vs. no LMWH will be accounted for in the statistical analysis. If a VTE is detected we will follow clinical guidelines and initiate

pharmacological VTE-treatment.

The comparator, **routine care**, lower limb immobilization will be administered by normal routine in the emergency department or in the outpatient clinic. Routine care include that the lower limb will be immobilized in an orthosis or a below-knee plaster cast according to local routines. At the 2 and 6 weeks visit the orthosis/plaster cast will be removed by a nurse who will document compliance. Subsequently, the patient will be examined by an orthopaedic surgeon (masked to the treatment allocation), who will document adverse events. At the 6-8 weeks visit the patient will also be sent for CDU-examination, which will document the main outcome. Patients will during the six weeks leg immobilization be weight-bearing with crutches or non-weight-bearing with crutches according to the preference of the orthopedic surgeon (blinded to the treatment group). Weight-bearing will be recorded and accounted for in the statistical analysis.

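### Patient-reported scores cannot confirm a long-term effect of IPC on VTE, and no VTE recording is described after the scan at 6 to 8 weeks

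*Combined protocol and SAP*

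**What the plan says.** The Outcome paragraph of Study Design (PICO) gives the patient-reported outcome measures (PROMs) a confirmatory role for VTE as well as for healing: "A long-term effect of IPC on VTE and healing will be confirmed by the secondary patient-reported outcome measures (PROM". The reason offered in the next sentence is that the investigators have data suggesting an effect of asymptomatic DVT on PROMs at one year. The size of that effect is not given.

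VTE itself is measured once, around the end of treatment:

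- Treatment period (Intervention): "Patients will during the six weeks of lower limb immobilization receive bilateral calf IPC".
- Primary outcome (Purpose and Aims): "The primary outcome measure is the VTE-incidence at the end of immobilization, i.e. about at six weeks". Variables and measures defines it as DVT "assessed at six weeks of immobilization by screening compression duplex ultrasound (CDU), or symptomatic pulmonary embolism detected by computer tomography".
- Primary question (Research question): whether IPC can "reduce the incidence of VTE up to the end of immobilization, i.e. 6-8 weeks".
- Scan, IPC arm (Intervention): "At the 6 weeks visit the patient will also be sent for CDU-examination, which will document the main outcome".
- Scan, control arm (Comparator): "At the 6-8 weeks visit the patient will also be sent for CDU-examination, which will document the main outcome".

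The follow-up described after that consists of PROMs at 6 and 12 months and the heel-rise test at one year (Variables and measures).

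Survey of the Field reports the group's earlier trial in Achilles tendon rupture (ATR): DVT in 21% with IPC against 37% in controls at 2 weeks, and then "IPC intervention ended at two weeks, and thus at 6 weeks the DVT-rate was 50% in both groups".

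**The concern.** The sentence sets a rule of inference: if PROMs are better at one year, a long-term effect on VTE counts as confirmed. That VTE lowers a score does not mean that a higher score shows fewer VTEs. IPC is expected to act on the same scores through tissue healing, which is one of the trial's secondary questions. DVTs found at the scan will be treated, so later scores also reflect that treatment.

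At stake is a claim of lasting VTE prevention resting on data that contain no VTE observation after about week 6 to 8. The earlier trial shows why persistence should not be taken for granted, because there a difference present while IPC was in use was gone four weeks after it stopped.

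**Working it through.** **1. Is VTE recorded after the scan?** I looked for any later source.

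- Adverse events and adherence are collected at 2 and 6 weeks. The listed events are skin damage, reasons for stopping IPC, and falls with injury; VTE is not among them (Variables and measures).
- The Outcome paragraph mentions major outcome events that will be supplied, but gives no definition and no time window.
- Longer-run effects in the economic analysis come from a decision-analytic model.
- No later scan, VTE form, VTE question or registry link is described.

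**2. The plan's own power figure.** Inputs from Estimated sample size and power: 1400 patients, 10% drop-out, 28% versus 20%, alpha 0.05 (taken as two-sided; the plan does not say). Allocation is 1:1.

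- Evaluable per arm: 1400 × 0.9 / 2 = 630.
- Pooled standard error: √(2 × 0.24 × 0.76 / 630) = 0.0241. Unpooled: √((0.28 × 0.72 + 0.20 × 0.80) / 630) = 0.0240.
- Power: Φ((0.08 − 1.96 × 0.0241) / 0.0240) = 91.5%, against the stated 90%.

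The figure reproduces. It concerns the comparison at the end of immobilization and says nothing about later VTE.

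**3. How much of a PROM difference can run through VTE?** Suppose each VTE lowers the score by L points on average, equally in both arms. The VTE-mediated mean difference is then (0.28 − 0.20) × L = 0.08 × L.

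The plan powers PROMs for 10 points on 0-100 scales. Producing that through VTE alone needs L = 10 / 0.08 = 125 points, more than the whole scale. The ankle-fracture subgroup assumption (25% versus 17%) gives the same answer. The most favourable case in the plan is the ATR subgroup (50% versus 35%): L = 10 / 0.15 = 67 points per VTE. That is possible on the scale, but nothing in the documents supports a loss of that size.

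**4. Could PROMs show a VTE-mediated difference of realistic size?** The documents give neither L nor a standard deviation (SD), so both are assumed: L of 5, 10 and 20 points, SD of 15 to 25. With 630 per arm, the standard error is SD × √(2/630), and power is Φ(difference / standard error − 1.96), counting only results in favour of IPC.

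| Assumed loss per VTE | Between-arm difference | Power, SD 25 to SD 15 |
|---|---|---|
| 5 points | 0.4 | 5% to 7% |
| 10 points | 0.8 | 8% to 16% |
| 20 points | 1.6 | 20% to 47% |

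A significant PROM difference would therefore mostly reflect something other than VTE, and a null PROM result would not count against a lasting VTE effect.

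**5. What the earlier trial shows.** The difference was 37 − 21 = 16 points at 2 weeks and 50 − 50 = 0 points at 6 weeks. IPC had stopped at 2 weeks. Survey of the Field goes on to say that IPC throughout the six-week immobilization remains to be tested, which implies that the leg was still immobilized when the rates converged.

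**The case against.** The strongest reply is that this is one sentence of rationale. The sentence after it can be read as treating PROMs as the downstream consequence of DVT for the patient. The statistical analysis plan contains only group comparisons of scores, with no estimand or test for long-term VTE, and the secondary research question links PROMs to healing and patient outcome. The primary question already stops at the end of immobilization. All of this is correct, and it limits the point to what may be concluded. It does not remove the sentence, which names VTE separately from healing and speaks of confirmation.

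A reader might go further and infer that the convergence seen in the earlier trial would go undetected here, and that its size is 16 points. The documents do not support that. The earlier convergence fell between weeks 2 and 6, apparently during continued immobilization. This trial extends IPC over that period and scans at its end, so the same convergence would be seen, including in patients who stop IPC early. Only a catch-up after IPC and immobilization end together would be missed. The documents give no evidence on whether that occurs or how large it might be.

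It can also be objected that asking about symptomatic VTE later would not settle the matter. It would miss asymptomatic DVT, which the scan includes. The plan itself says that an effect on clinical pulmonary embolism would take several tens of thousands of patients. Treatment of DVTs found at the scan would also disturb the later comparison between arms. That stands, and it is why such data should be descriptive only.

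**Conclusion.** The point holds in a limited form. PROMs cannot confirm a long-term effect of IPC on VTE: they do not measure it, IPC is expected to change them by another route, and no VTE data after 6 to 8 weeks are described. With 28% versus 20%, VTE could account for only 0.08 points of mean difference per point lost per VTE, so the 10-point target could not arise from VTE alone. This rests on an equal average loss per VTE in both arms and on the plan's own rates. The power range in the table rests additionally on assumed losses and SDs.

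The primary analysis, its sample size and its stated question are not affected. The earlier trial motivates caution about persistence, but it does not size any catch-up after week 6.

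A related wording fault is that the Outcome paragraph places the primary outcome at a time that can be read as six weeks after immobilization ends. Purpose and Aims, Variables and measures, and Intervention all point to the end of immobilization.

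**What to change.** 1. In the Outcome paragraph, delete VTE from the PROM sentence and state that PROMs assess healing and patient outcome only. State also that no VTE claim will be made beyond the end of immobilization. This costs nothing except a broader claim that the data could not support.
2. Reconcile the time of the primary outcome in the Outcome paragraph with Purpose and Aims, Variables and measures, and Intervention. The scan time given for the two arms (6 weeks in one, 6 to 8 in the other) should be reconciled in the same edit.
3. Optional and cheap: add to the 6- and 12-month questionnaires one question on symptomatic VTE since the scan, confirm positive answers from records, and report the results by arm without a test. The cost is some extra data collection and record checks at 20 or more hospitals, limited to patients who answer yes. The Outcome paragraph describes only the one-year visit, with questionnaires sent home if it is missed, so the plan should also say how the 6-month questionnaire is collected. The report should say that these data miss late asymptomatic DVT, have low power, and are affected by anticoagulation of VTE found at the scan.
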